STUDY DOCUMENT

Official Study Title:

The Effect of Prone Position on Oxygen Saturation, Blood Gas Parameters, and Respiratory Rate in Intensive Care Patients with COVID-19-induced ARDS

NCT Number: NCTXXXXXXX

Document Type: Study Protocol

Document Date: 26 May 2025

STUDY PROTOCOL

1. Official Title

The Effect of Prone Position on Oxygen Saturation, Blood Gas Parameters, and Respiratory Rate in Intensive Care Patients with COVID-19-induced ARDS

2. Brief Title

Effect of Prone Position in COVID-19 ARDS Patients

3. Principal Investigator(s)

- [name], RN, Ph.D. – Diyarbakır Provincial Health Directorate
- [name]. [name], Ph.D. – Inonu University Faculty of Nursing

4. Study Sites

General and Intermediate Intensive Care Units, Eastern Turkey

5. Study Period

Start Date: April 1, 2021

End Date: August 30, 2021

6. Background and Rationale

ARDS is a common complication of severe COVID-19, associated with high mortality. Prone positioning has been shown to improve oxygenation and lung compliance in ARDS. This study investigates its short-term effectiveness in non-intubated patients.

7. Objectives

To evaluate the impact of a 30-minute prone position on:

- Oxygen saturation (SpO₂, SaO₂, PO₂)
- Respiratory rate
- Blood gas parameters (pH, PCO₂, Lactate, Sodium)

8. Study Design

Randomized controlled trial

Parallel group, repeated measures (6 total timepoints)

1:1 allocation (n = 90, 45 per group)

9. Eligibility Criteria

Inclusion Criteria:

- Age ≥ 40
- ICU hospitalization for COVID-19-induced ARDS
- Intubated and responsive to assessment

Exclusion Criteria:

- Sensory impairments (vision/hearing)

- Cognitive impairments
- Patients who died or no longer required ICU during study

10. Intervention

Experimental Group: 30 minutes prone position once daily for 2 days

Control Group: Supine standard care

11. Outcomes

Primary Outcome:

- Change in oxygen saturation (SpO_2) post-prone positioning

Secondary Outcomes:

- Respiratory rate
- Arterial blood gas values (SaO_2 , PO_2 , PCO_2 , pH, lactate, sodium)

12. Randomization

Simple randomization by drawing lots

Allocation ratio 1:1

13. Blinding

Open-label (no blinding)

14. Statistical Methods

Paired and independent t-tests

Wilk's Lambda

Cohen's d for effect size

SPSS used for data analysis

15. Ethical Considerations

Approval: Gazi Yasargil Training and Research Hospital Ethics Committee (15.01.2021 / No: 626)

Verbal and written consent obtained

Conducted per Declaration of Helsinki

16. Data Sharing Plan

Available upon reasonable request from the corresponding author.

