# STATISTICAL ANALYSIS PLAN

## 1. Study Identification

Official Title: The Effect of Prone Position on Oxygen Saturation, Blood Gas Parameters, and Respiratory Rate in Intensive Care Patients with COVID-19-induced ARDS

NCT Number: NCTXXXXXXXX

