## 4. Sample Size Justification

A total of 90 patients (45 per group) were selected using 95% confidence level, 5% margin of error, and an effect size of 0.70.

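### Protocol Section 6 describes a trial in non-intubated patients, but the Section 9 inclusion criterion requires intubation, and nothing else in the Protocol or SAP settles which population was studied.

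*Protocol*

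**What the plan says.** Protocol Section 6 (Background and Rationale) gives the target population when it introduces prone positioning: "This study investigates its short-term effectiveness in non-intubated patients".

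Protocol Section 9 (Eligibility Criteria) lists three inclusion criteria: an age limit, an ICU stay for COVID-19-induced ARDS, and "Intubated and responsive to assessment". Its exclusions include "Sensory impairments (vision/hearing)" and "Cognitive impairments".

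Protocol Section 15 records "Verbal and written consent obtained", without saying who gave it.

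The title, repeated in SAP Section 1, refers only to "Respiratory Rate in Intensive Care Patients with COVID-19-induced ARDS". The sample size is given in Protocol Section 8 as "1:1 allocation (n = 90, 45 per group)", and SAP Section 4 agrees: "A total of 90 patients (45 per group) were selected". SAP Section 5 draws lots among eligible admissions without restating the criteria, and SAP Section 9 defines the analysis set by completion of the six measurements.

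**The concern.** An inclusion criterion is the operative definition of the trial population. Here it admits only patients whom the rationale places outside the study. Both statements are current text in one document dated 26 May 2025; neither comes from an amendment log, so one cannot be read as superseding the other.

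At stake is the meaning of the primary result. A change in SpO2 after prone positioning describes a particular kind of patient, and a reader of these documents cannot tell whether those patients were intubated. The SAP inherits the problem because it relies on eligibility as defined elsewhere.

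**Working it through.** The point is textual and the plan offers no figure to reproduce. The check has three steps.

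**1. The two statements side by side.**

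| Place | Airway status |
|---|---|
| Protocol Section 6, population the study addresses | Not intubated |
| Protocol Section 9, inclusion criterion | Intubated |

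The categories exclude each other at enrolment. No passage defines a mixed population or says that one section overrides the other.

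**2. Search for anything that settles it.** A case-insensitive search of the supplied text gives:

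| Word stem | Protocol | SAP |
|---|---|---|
| intubat | 2 (Sections 6 and 9) | 0 |
| ventilat | 0 | 0 |
| airway | 0 | 0 |

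The title, objectives, design, exclusions, intervention and outcomes do not state airway status. Neither do the SAP sections on randomization, missing data and analysis population.

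Several features sit more easily with awake patients: responsiveness to assessment, the sensory and cognitive exclusions, verbal consent, and respiratory rate as an outcome. None of them states airway status, so they are hints and not a resolution.

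**3. How much of the sample is affected.** The input is N = 90 (Protocol Section 8; SAP Section 4). Let k be the number enrolled who were intubated. Then k patients lie outside the Section 6 population and 90 − k fail the Section 9 criterion.

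| Case | k, outside Section 6 | 90 − k, failing Section 9 |
|---|---|---|
| Section 9 followed throughout | 90 (100%) | 0 |
| Section 6 followed throughout | 0 | 90 (100%) |
| Mixed enrolment | between 0 and 90 | the remainder |

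In every case k + (90 − k) = 90, so each patient contradicts exactly one of the two sections. The documents give no counts by airway status, so k is unknown.

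**The case against.** The strongest reply is that this is an obvious slip: a missing negative in Section 9, with the surrounding criteria and consent wording pointing to awake patients. On that view the harm is one of labelling. Enrolment closed on 30 August 2021 (Protocol Section 5), randomisation still protects the comparison, and no test or endpoint in the SAP would change. Calling it a mandatory fix might then seem too strong.

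Part of this stands. A slip is plausible, and the point does not undermine the between-arm comparison. Mixed enrolment could leave airway status unbalanced between arms by chance, but it would not introduce systematic bias. The 100% figure also follows by definition from two exclusive categories; it shows that the conflict has no partial reading, and it is not an estimate of anything.

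Two things do not follow. First, the hints do not establish the slip, and a reader should not have to guess an inclusion criterion. If it is a slip, the public eligibility rule says the opposite of what was meant and needs correcting all the more. Second, closed enrolment does not make the matter moot. The documents date from 2025 and are the record against which the results will be read.

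Whether the sample-size inputs suit one population better than the other cannot be judged, because SAP Section 4 does not say where its effect size of 0.70 comes from. The point does not depend on it.

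**Conclusion.** The concern holds. Sections 6 and 9 of the Protocol name mutually exclusive populations, and nothing in the supplied text resolves the conflict. It touches all 90 planned patients: all of them contradict Section 6, or all contradict Section 9, or they divide between the two. Which applies is unknown.

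The consequence is confined to the population described and to generalisability. Until the records are checked, the SpO2 result cannot be assigned to a defined population, which is why the point must be fixed although the repair is small.

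The conclusion rests on the supplied text. It assumes only that the part of the SAP removed before its Section 1 does not address airway status. It takes no position on which section is right.

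**What to change.** 1. Check Protocol Sections 6 and 9 against the version the ethics committee approved (Protocol Section 15, dated 15.01.2021) and against the enrolment records, without presuming which wording is correct.
2. Issue a dated correction so that both sections name the same population.
3. Add a row to the baseline table giving airway status at randomisation by arm. It will read 0% or 100% in both arms if one section was followed throughout; any other value shows mixed enrolment, in which case neither section describes the sample.
4. Limit the conclusions to the population so confirmed.

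No further analysis is asked for. The cost is a records check, one correction and one table row, assuming that airway status at randomisation can be retrieved. The correction changes the record and the conclusions, not the conduct of the trial. The downside for the sponsor is that the result may apply to a different or narrower population than Section 6 states.

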## 9. Analysis Population

Only patients who completed all six measurements were included in the analysis.

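### No check before the lot on whether a patient can be placed prone: with completers-only analysis, this opens a route to one-sided post-randomisation loss of unknown size and direction

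*Protocol*

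**What the plan says.** Protocol section 9 lists three exclusions: "Sensory impairments (vision/hearing"), "Cognitive impairments" and "Patients who died or no longer required ICU during study". The third can only be applied after entry. The inclusion criteria are age, an intensive care stay for COVID-19 ARDS, and "Intubated and responsive to assessment". None of these addresses whether the patient can be turned.

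Protocol section 10 assigns "30 minutes prone position once daily for 2 days" to one arm and "Supine standard care" to the other. Section 13 makes the trial open-label.

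SAP section 5 draws lots among eligible admissions, so the section 9 list is the only screen before allocation. SAP section 8 excludes patients who died, were discharged or dropped out, and imputes nothing. SAP section 9 adds: "Only patients who completed all six measurements were included in the analysis". Neither document says what happens to a patient who is allocated to prone and is not turned.

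**The concern.** The prone arm requires a manoeuvre on two days that the control arm never requires. If a candidate cannot be placed prone, nothing in the plan finds this out before the lot. A control patient with the same condition stays supine, and that condition does not stop the patient completing the schedule. A patient who draws prone may not be turned, may be treated as a dropout or fall short of six measurements, and then leaves the analysis. The judgement that the patient cannot be turned is also made with the arm known.

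The same kind of patient could thus be kept in one arm and removed from the other, and the arms would no longer be comparable as randomised. The SpO2 comparison and the secondary blood gas comparisons are exposed in the same way.

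**Working it through.** **The plan's own figure.** SAP section 4 gives 45 per group for an effect size of 0.70 at 95% confidence, without power or sidedness. With n = 2(z_α + z_β)²/0.70²:
- one-sided 0.05, power 95%: 2(1.645 + 1.645)²/0.49 = 44.2, so 45;
- two-sided 0.05, power 90%: 2(1.960 + 1.282)²/0.49 = 42.9, so 43.

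The figure can be reached under reasonable settings and is not disputed. The 45 and the 0.70 serve below as the arm size and the yardstick.

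**What can happen to a prone-arm patient who cannot safely or practically be turned.**
1. Turned anyway and measured six times: stays in the analysis, so no selection.
2. Not turned but measured on the same six-point schedule as the controls: meets SAP section 9 and stays. The effect is diluted.
3. Not turned and lost under SAP section 8 or 9: one-sided loss.

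Only the third produces selection bias.

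**Size of route 3.** Assumed inputs, because the documents give neither: k of 45 prone-arm patients are lost, and their mean SpO2 change is D standard deviations worse than that of the remaining patients. No control is assumed lost for the same reason. The prone-arm mean then moves by (k/45) × D.

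| k | D | Shift (SD) | Share of 0.70 | Type I error |
|---|---|---|---|---|
| 4 | 0.5 | 0.044 | 6.3% | 0.055 |
| 4 | 1.0 | 0.089 | 12.7% | 0.070 |
| 9 | 0.5 | 0.100 | 14.3% | 0.073 |
| 9 | 1.0 | 0.200 | 28.6% | 0.146 |

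The last column is for a nominal two-sided 0.05 test by normal approximation, with 45 − k prone and 45 control patients: standard error √(1/(45 − k) + 1/45), which is 0.216 for k = 4 and 0.224 for k = 9.

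If 45 is the number left after losses, the share lost is k/(45 + k). The shifts become 0.041 to 0.082 SD for k = 4 and 0.083 to 0.167 SD for k = 9. With k = 0 or D = 0 the shift is zero. With D negative it runs against prone.

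**Size of route 2.** If k of 45 are kept, not turned, and respond as controls do, the effect becomes 0.70 × (45 − k)/45. That is 0.64 for k = 4 and 0.56 for k = 9. Two-sided power with 45 per arm falls from 0.91 to 0.86 and 0.76.

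**With a check before the lot.** Patients judged unsuitable leave before allocation, so this source of one-sided loss is removed. To randomise 90 suitable patients when 10% or 20% are unsuitable (assumed), 90/0.90 = 100 or 90/0.80 = 112.5, so 113, must be assessed.

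**The case against.** A reader might infer that the SpO2 comparison is biased towards prone. The documents do not support that. No section shows that any such patient was enrolled, turned or lost, and no losses by arm are given.

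Nor do they establish that an unturned patient lacks the required measurements. Controls supply all six without ever lying prone, so an unturned patient could be measured on the same schedule. That gives dilution, which works against prone.

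The direction is also assumed. Patients who cannot be turned may well be less stable, but the outcome is change in SpO2, and a worse level does not imply a worse change. If they are less stable, some of their counterparts in the control arm will die and be removed as well, which narrows the asymmetry.

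It can be said, too, that the completers-only rule does the damage: with everyone measured and analysed as allocated, this selection bias would disappear under the same eligibility list. That is largely right, and the two should be dealt with together. But death and discharge can remove patients from either arm, whereas inability to be turned can do so only in the prone arm. The missing check adds that one-sided route.

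Finally, Protocol section 5 ends the study period on 30 August 2021 and both documents are dated 26 May 2025. A pre-lot check cannot change who was enrolled. This stands, and it limits what can be done for this trial to retention and reporting.

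A further reading, that the plan sends unsuitable patients into a harmful procedure, goes beyond the documents: they are silent on bedside judgement, and silence does not show that it was absent.

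**Conclusion.** The concern holds as a risk. The plan has no criterion on whether a patient can be placed prone and no check before the lot; with the dropout exclusion and the completed-all-six rule, this allows a post-randomisation loss that can arise in the prone arm only. Its size and direction are unknown. Under the assumed 4 to 9 of 45 lost and a gap of 0.5 to 1.0 SD in SpO2 change, the shift is 0.04 to 0.20 SD, or 6% to 29% of the planned 0.70. The upper end needs a fifth of the arm to be lost, a full 1 SD gap, and no matching loss among controls.

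One inconsistency makes the risk harder to judge. Protocol section 6 describes the patients as non-intubated, while section 9 requires "Intubated and responsive to assessment". These must be reconciled, because they determine who was to be turned.

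**What to change.** **Protocol section 9.** State that suitability for either allocation, as judged by the treating team under the site's existing practice, is assessed and recorded for every candidate before the lot is drawn. No clinical criterion is proposed here. With enrolment over, this matters for any further recruitment. If such an assessment was made in practice, the protocol should say so.

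**Patients already enrolled (SAP sections 8 and 9).**
- Keep those allocated to prone but not turned in their assigned arm, with whatever scheduled measurements exist, and do not drop them for missing some of the six. The analysis must therefore accept incomplete series.
- Report by arm the numbers allocated, not turned (with reasons) and lost.
- Repeat the SpO2 comparison without such patients in both arms only if the condition can be classified from pre-allocation records, blind to arm. Nothing in the documents shows that such records exist for controls. If they do not, say so and omit this analysis.

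**Cost.** A slightly narrower population where the check applies, a record check, and one extra analysis. Keeping unturned patients may dilute the estimated effect, as shown above; that is the price of comparing the arms as randomised.

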# STATISTICAL ANALYSIS PLAN

## 1. Study Identification

Official Title: The Effect of Prone Position on Oxygen Saturation, Blood Gas Parameters, and Respiratory Rate in Intensive Care Patients with COVID-19-induced ARDS

NCT Number: NCTXXXXXXXX

## 2. Objectives

To determine the impact of prone positioning on:

- Oxygen saturation (SpO2, SaO2, PO2)
- Respiratory rate
- Blood gas parameters (pH, PCO2, Lactate, Sodium)

## 3. Study Design Summary

This is a randomized controlled trial with a parallel group and repeated measures over six time points.

## 4. Sample Size Justification

A total of 90 patients (45 per group) were selected using 95% confidence level, 5% margin of error, and an effect size of 0.70.

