## 5. Randomization

Random assignment was done by drawing lots from every four eligible ICU admissions each day.

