## 8. Handling of Missing Data

Patients who died, were discharged, or dropped out were excluded. No imputation was used for missing values.

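### Analysing only completers of an allocated 90, with no loss allowance or replacement rule, undoes the randomised SpO2 comparison if anyone was lost after the draw

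*SAP*

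**What the plan says.** **Number of patients.** SAP 4 states that "A total of 90 patients (45 per group) were selected". Protocol 8 has "1:1 allocation (n = 90, 45 per group". SAP 5 describes the draw ("Random assignment was done by drawing lots from every four eligible ICU admissions each day") but gives no total drawn.

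**Removal of patients.** Protocol 9 lists among its exclusion criteria "Patients who died or no longer required ICU during study". SAP 8 says "Patients who died, were discharged, or dropped out were excluded" and adds that nothing was imputed. SAP 9 says "Only patients who completed all six measurements were included in the analysis".

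**Not stated in either document.** A loss allowance, a replacement rule, the number lost and the number analysed.

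**The concern.** Death, leaving the ICU and dropping out can all happen after a patient's lot has been drawn. Protocol 9 treats the first two as ineligibility, and SAP 8 and 9 take all three out of the analysis. If this removed anyone, one of two things followed:

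- 90 were randomised and fewer than 90 were analysed, a number that is neither given nor planned for; or
- lost patients were replaced, and more than 90 were randomised.

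In both cases the primary SpO2 comparison is between patients selected by what happened after randomisation. The losses need not be alike in the two groups. The trial is open-label (Protocol 13), and only the experimental group has a prone session to stop. Loss of precision is the smaller cost; possible bias in the primary comparison is the larger one.

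**Working it through.** **Step 1. What the 90 allows for.** Inputs: 45 per group and an effect size of 0.70 (SAP 4), read as Cohen's d because SAP 7 names that index, and alpha 0.05 from the 95% confidence level. Power and sidedness are not given, so 90 cannot be strictly reproduced. For a two-group t-test at d = 0.70:

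- One-sided, 95% power needs 45 per group, leaving no room for loss.
- Two-sided, 90% power needs 44 per group, leaving 1 of 45 (2%).
- Two-sided, 80% power needs 34 per group, leaving 11 of 45 (24%).

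No loss allowance can therefore be inferred from the number itself.

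**Step 2. Precision and power if 90 were randomised.** The documents give no loss rate, so 10% and 20% are assumed: 45 × 0.9 = 40.5, taken as 40, and 45 × 0.8 = 36 per group. The 95% CI half-width is t(0.975, 2n − 2) × √(2/n), in SDs. Power is from the noncentral t, two-sided 5%, with noncentrality 0.70 × √(n/2).

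| n per group | Half-width (SD) | Noncentrality | Power |
|---|---|---|---|
| 45 | 0.419 | 3.32 | 90.7% |
| 40 | 0.445 | 3.13 | 87.1% |
| 36 | 0.470 | 2.97 | 83.4% |

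SAP 4 does not say which SD scales the 0.70. If it is the SD of SpO2 at a single time point, a change score with correlation r between time points has d = 0.70/√(2(1 − r)):

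| r | d | Power, 45 per group | Power, 36 per group |
|---|---|---|---|
| 0 | 0.495 | 64% | 54% |
| 0.3 | 0.592 | 79% | 70% |
| 0.5 | 0.700 | 91% | 83% |
| 0.7 | 0.904 | 99% | 97% |

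The documents give no r. The drop from a 20% loss is 2 to 10 points over this range.

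**Step 3. Bias in the completers.** Assumptions: 45 completers in each group, no true effect, losses in one group only, and a two-sided 5% t-test. The affected group starts from 45/0.9 = 50 (5 lost) or 45/0.8 = 56.25, taken as 56 (11 lost). Figures are from 40,000 simulated trials per case.

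| Who is lost | Mean shift, 5 of 50 / 11 of 56 | False-positive rate |
|---|---|---|
| Exactly the lowest values (worst case) | about 0.19 / 0.34 SD | about 17% / 43% |
| Loss correlates 0.5 with the outcome | about 0.10 / 0.17 SD | about 7% / 13% |
| About half lowest, half highest | close to zero | about 7% to 8% |

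In the last row the rate stays slightly above 5% because cutting both tails shrinks the visible spread in that group. Against an effect of 0.70 on the same scale, the worst-case shifts are 0.19/0.70 = 27% and 0.34/0.70 = 49%.

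**The case against.** **The 90 are most naturally the number randomised.** Protocol 8 attaches the figure to allocation in its design section. A reader might infer that 45 against 45 is a quota of completers, topped up by replacement so that a trial with losses looks whole. The documents do not support that: no passage mentions replacement, and "were selected" in SAP 4 is too loose to show it. This objection stands. What remains is that the allocated number is not reconciled with the removal rules.

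**Nothing shows that anyone was lost.** SAP 8 is in the past tense, in a document dated 26 May 2025 for a study that ended on 30 August 2021, so a reader might take it as a report of actual exclusions. It can equally be a rule phrased in the past tense. The condition is described as "associated with high mortality" (Protocol 6), but that is about ARDS in general, and the intervention is short: "Experimental Group: 30 minutes prone position once daily for 2 days". Loss is plausible, not shown.

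**Losses may offset each other.** SAP 8 removes discharged patients as well as those who died. If the discharged had better oxygenation, removing them works against the loss of low values. This also stands. The 43% figure is an extreme, not an expectation, and the documents show neither the direction of any bias nor that losses differed between groups.

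**Patient counts belong in the results report.** That is fair for the counts. It does not reach the rule in SAP 8 and 9 that sets aside randomised patients, which is a choice made in the plan.

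**Conclusion.** The point holds in a limited form. The stated rules remove randomised patients for later events, with no loss allowance and no replacement rule, and they can bias the primary SpO2 comparison. The change should be made; confidence is medium because the size depends on losses that the documents do not report.

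If nobody was lost, there is no effect. If 10% or 20% of 90 were lost, the loss of precision is modest. The bias ranges from close to zero, when low and high values are lost about equally, to about a third of an SD in the worst case of one-sided loss of 11 of 56. The documents do not establish hidden replacement, unequal losses or an inflated result.

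**What to change.** - **SAP 8 and 9 (and the method in SAP 7).** Make the primary analysis all randomised patients with at least one SpO2 value, in the group drawn, using a repeated-measures mixed model. Report the between-group difference with its 95% CI. Keep the completers analysis as a sensitivity analysis.
- **Protocol 9.** Remove death and no longer needing the ICU as grounds for excluding patients who have already been randomised.
- **Rank-based sensitivity analysis.** The mixed model treats SpO2 after death as merely missing. Add an analysis with death ranked lowest and a stated rank for patients who left the ICU alive.
- **SAP 4 and Protocol 8.** State whether 90 is the number randomised or completing, and whether lost patients were replaced. From the lot-drawing records, report per group the numbers randomised, died, discharged, dropped out and analysed. If nobody was lost, one sentence saying so closes the point.
- **Labelling and fallback.** Label the added analyses post hoc. If the excluded patients' values were not kept, report the counts and bounds on the difference.

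The cost is retrieving the allocation log and any partial data, one mixed model and one rank analysis; no new patients are needed. The analysed number may then differ from 90, and the SpO2 difference may be smaller.

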## 7. Statistical Methods

- Descriptive statistics: mean, standard deviation, frequency, and percentage
- Inferential statistics: Wilk's Lambda for repeated measures, paired t-tests, independent t-tests
- Effect size: Cohen's d
- Software: SPSS v22

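### Does the sample size paragraph's use of precision terms leave 90 patients unjustified for an effect size of 0.70?

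*SAP*

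**What the plan says.** SAP section 4 (Sample Size Justification) is one sentence: "A total of 90 patients (45 per group) were selected using 95% confidence level, 5% margin of error, and an effect size of 0.70". The Protocol repeats only the numbers, under Study Design: "1:1 allocation (n = 90, 45 per group".

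SAP section 7 (Statistical Methods) lists the tests as "Inferential statistics: Wilk's Lambda for repeated measures, paired t-tests, independent t-tests" and names one effect measure, "Effect size: Cohen's d". No sidedness is given there or in Protocol section 14. SAP section 6 makes the primary outcome the change in SpO2 across the six time points. On who is analysed, SAP section 9 says: "Only patients who completed all six measurements were included in the analysis".

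Neither document states a power, the test used for sizing, the contrast to which 0.70 applies, or an allowance for losses. Neither says whether 90 is the number randomised or the number who completed.

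**The concern.** The terms in "95% confidence level, 5% margin of error" belong to a survey-type precision calculation, and the 5% is attached to no quantity. Sizing a comparison of two means needs a significance level, sidedness, power and a standardised difference, and only the last is clearly present.

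If the two percentages are taken as power and significance level, 45 per group comes out exactly, but only for a one-sided test. No one-sided test is declared, and the two-sided requirement would be larger. The paragraph is also silent on losses, although only complete cases are analysed, and a single two-sample effect size is not the natural input for a multivariate test over six time points.

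At stake would be the reading of a null result: someone who believed the trial had 95% power for 0.70 SD would overstate what it could rule out.

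**Working it through.** **Inputs.** From the documents: 45 per group, 1:1, and an effect size of 0.70 (SAP section 4; Protocol section 8). Assumed: 0.70 is Cohen's d between arms, since that is the only effect measure SAP section 7 names; SD = 1, since the effect is standardised; significance level 0.05, from the 95% confidence level. Power and sidedness are unstated, so several values are tried.

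**Can the stated figure be reproduced?** Not from the stated inputs alone, because power is missing. With power and sidedness supplied, the normal formula per group is n = 2(z_α + z_power)² / d², with z_α replaced by z_α/2 for a two-sided test:

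- One-sided 5%, 95% power: 2(1.645 + 1.645)² / 0.49 = 44.2, so 45. The exact t calculation gives 44.87, so 45 per group and 90 in total.
- Two-sided 5%, 90% power: 2(1.960 + 1.282)² / 0.49 = 42.9, so 43. Exact t gives 43.87, so 44 per group and 88 in total, two patients short of 90.
- Two-sided 5%, 95% power: 2(1.960 + 1.645)² / 0.49 = 53.0, so 54. Exact t gives 54.02, so 55 per group, which does not match.

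Two routes with a loss allowance also reach 45 per group:

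- Two-sided 5%, 85% power needs 38 (exact t), and 38 / (1 − 0.15) = 44.7, so 45.
- One-sided 5%, 90% power needs 36 (exact t), and 36 / (1 − 0.20) = 45.

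So the one-sided 95% reading is not the only route to 90. It is the sole match only if 95% is taken to be the power and no losses are assumed, and the SAP says neither.

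**Power of the stated design.** The noncentrality is 0.70 × √(45/2) = 3.320.

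- Two-sided: Φ(3.320 − 1.960) = 91.3%; exact t 90.7%.
- One-sided: Φ(3.320 − 1.645) = 95.3%; exact t 95.1%.
- Difference detectable with 80% power, two-sided: 0.60 SD.

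**The precision reading.** For a proportion at p = 0.5 with a five-point margin, n = 1.96² × 0.25 / 0.05² = 384.1, so 385. A finite-population correction brings this to 90 only for a population of about 117, a figure the documents do not give. For a mean difference with 45 per group, the 95% half-width is 1.96 × √(2/45) = 0.41 SD. Neither describes how a change in SpO2 would be sized, so the 385 shows that the term is out of place. It does not show that 90 is too few.

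**If 90 were randomised and some were not analysed.** The loss rates here are assumptions; the documents give none.

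| Assumed loss | Analysed per group | Two-sided power at d = 0.70 |
|---|---|---|
| none | 45 | 90.7% |
| about 10% | 40 | 87.1% |
| about 20% | 36 | 83.4% |
| about 30% | 31 | 77.4% |

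**A five-degree-of-freedom arm-by-time test.** Suppose the whole multivariate noncentrality equals that of one d = 0.70 contrast, λ = (45/2) × 0.70² = 11.025. Then power on F(5, 84) is 69%, or 57% with 72 patients analysed. Equality is the least favourable case: if 0.70 is the standardised difference in any within-patient change contrast, the multivariate noncentrality is at least this large, so these figures are floors. Without the time profile and the within-patient correlations, which are not given, the actual power cannot be computed.

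**The case for a change.** The best case for a change is that a reader cannot tell how 90 was reached. Several incompatible sets of assumptions lead to it, and they differ on sidedness, power and losses. Losses are foreseeable in this population: SAP section 8 removes patients who died, were discharged or dropped out, and Protocol section 9 lists death and no longer needing intensive care among its exclusions. If 90 were randomised, power at d = 0.70 falls to about 83% with a 20% loss. The primary outcome spans six time points, yet the sizing uses one number. Correcting this would take a paragraph and no patients.

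The first point stands: the justification is incomplete and one of its terms is misapplied. The others carry less weight.

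- The SAP states no power, so the 95% assurance it is said to imply comes from one reading of the text.
- The loss figures apply only if 90 is the number randomised. The exclusions, written in the past tense, are equally compatible with 90 being the number analysed. Even with a 20% loss, power stays above 80%.
- The figures for the six-time-point test rest on an assumed noncentrality and do not estimate this design's power.
- Writing in a two-sided test with 91% power would give the study a rationale that nothing in the documents shows to be the one used.

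**Conclusion.** No change is needed. The paragraph is loosely worded and omits inputs, but it promises no power that the design fails to deliver. Read in the ordinary way, with a 5% significance level and 0.70 as Cohen's d for one between-arm comparison, 45 analysed per group gives about 91% power two-sided and 95% one-sided. The conventional two-sided requirement for 90% power is 44 per group. The number is therefore adequate for the effect it names.

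This rests on three assumptions: that 0.70 is a between-arm Cohen's d, that the level is 0.05, and that 45 per group are analysed. If 90 is instead the number randomised, power would be 87%, 83% or 77% for assumed losses of about 10%, 20% or 30%. Whether analysing completers only could bias the comparison is a separate question that no sample size wording would settle.

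There is also nothing to gain. The Protocol gives 30 August 2021 as the end of the study and the SAP is dated 26 May 2025, so recruitment cannot respond to a revised calculation. What a null result rules out is read from the confidence interval for the arm difference, whatever section 4 says. New wording there would leave every analysis, estimate and conclusion as it is.
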